## **7.9. Audits and inspections**

For the purpose of compliance with applicable regulatory guidelines, it may be necessary for PATH or national or foreign regulatory authorities to conduct a site audit. This may occur at any time from study start to after the conclusion of the study.

The investigator agrees to allow the auditor direct access to all relevant documents and to allocate time to the auditor to discuss findings and any relevant issues.

National and foreign regulatory authorities may conduct a regulatory inspection of this study. If a regulatory authority requests an inspection, the investigator must inform PATH immediately about this request. The investigator agrees to allow the inspector(s) direct access to all relevant documents and to allocate time and the time of staff to the inspector(s) to discuss findings and any relevant issues.

## **8. ETHICAL ASSURANCE FOR PROTECTION OF HUMAN RIGHTS**

### **8.1. Ethical standard**

The investigator will ensure that this study is conducted in full conformity with the current revision of the Declaration of Helsinki, ICH-GCP, and/or with local regulatory requirements, whichever affords the greater protection to the participant.

### **8.2. Institutional review board**

The protocol will be reviewed and approved by all of the following bodies before recruitment begins:

1. Western Institutional Review Board (WIRB). PATH subcontracts its ethical review for clinical trials to WIRB.
2. The icddr,b RRC and ERC.

All amendments will be approved in writing by WIRB and the icddr,b RRC and ERC before implementation and paperwork are shared between partners, as appropriate. No deviations from, or changes to, the protocol shall be initiated without prior written IRB approval by both WIRB and icddr,b of an appropriate amendment from all responsible IRBs, except when necessary to eliminate immediate hazards to the participants or when the change(s) involves only logistical or administrative aspects of the study (e.g., change of telephone number, etc.).

The PI will sign the final approved protocol.

### **8.3. Informed consent process**

Prior to receipt of study vaccine, written informed consent will be obtained from a parent/guardian for all child participants. Informed consent documents will embody the elements of consent as described in the Declaration of Helsinki and the ICH Harmonized Tripartite Guidelines for GCP. The consent form will be in Bangla.

Original Informed Consent Forms must be kept on file by the investigator for possible inspection by regulatory authorities and PATH. The participant or the participant's legally acceptable representative must receive a copy of the signed and dated Informed Consent Form(s), and any subsequent updates or amendments. The study monitor shall check the documentation of the individual Informed Consent Form(s) during each monitoring visit.

Parents will initially be briefed about the study by a field worker, since they are known to the household and routinely inform participants and parents/guardians about vaccine trials and surveillance.

In the study clinic, the medical officer will ask if the child and parents/guardians have any questions about the study, read the informed consent form, and then conduct informed consent. One parent/guardian must sign the informed consent form. If the parent/guardian is illiterate, they may provide a thumb impression instead and an impartial literate witness (hierarchically independent of the PI and not specified on the list of trial contributors) will be present and attest to the parent/guardian consent. Consent will follow site-specific practices and be described in an SOP.

#### **8.4. Inclusion of women and children**

Children of any race/ethnicity and residing in the study area will be recruited for participation in the study. No special recruitment methods will be used to ensure certain levels of participation by any specific minorities residing in the source population. Investigators will emphasize during information sessions that girls and boys are at equal risk of JE and its complications.

#### **8.5. Participant confidentiality**

##### **8.5.1. Confidentiality of data**

By signing the protocol, the investigators agree that the study protocol, documentation, data, and all other information generated regarding the vaccines will be held in strict confidence. The investigators may divulge such information within regulatory restrictions and ethical considerations only to ethical review committees or similar expert boards or committees, and their affiliated institutions and employees, only under an appropriate understanding of confidentiality with such board or committee, and their affiliated institutions and employees. No information concerning the study or the data may be released to any unauthorized third party without prior written approval of PATH. Any regulatory agency deemed appropriate may consult study documents in order to verify case report form data. Investigators will ensure that all employees involved in the study respect the same rules.

Documents and data pertaining to the study will be kept in a locked cabinet under the responsibility of the investigator. PATH will conduct periodic monitoring visits to ensure that the data is safe and stored in this secure place and that only those authorized study staff have access to the data. Study data will be kept for five years after completion of the study.

Study participants will not be reported by name in any report or publication resulting from data collected in this study.

##### **8.5.2. Confidentiality of patient records**

Participant confidentiality is strictly held in trust by the participating investigators, their staff, and the sponsor(s) and their agents. This confidentiality pertains to a participant's personal and health information and extends to information on any biological specimen of the participant. Medical information about individual participants obtained during the course of this study is confidential and may not be disclosed to third parties, except authorized monitors, sponsors, auditors or inspectors. Confidentiality will be ensured by the use of participant numbers coding for the identification of each participant's personal, health, and specimen information. Access to this linkage and other confidential data will be strictly controlled.

The investigators will keep individual results confidential to the extent permitted by law. Information will not be released to anyone other than the participant, their parent or guardian, or their medical provider, unless required to do so by law.

### **8.5.3. Notification of primary care physician**

If agreed by the participant or participant's legally acceptable representative, the investigator shall notify the participant's primary care physician, if applicable, of participation in the study. Participant's involvement in the study and study team contact numbers will be reported into the participant's identification card as applicable.

### **8.6. Study discontinuation**

There are no expected reasons that would result in suspension and/or termination of the study. Unexpected reasons include:

- New safety data about the investigational product resulting from this or any other trial becomes available.
- The sponsor or ERC overseeing this study suspends and/or terminates the study for any justified reason, including the event that early safety data reveal an unusually high rate of SAEs or in the event study conduct fails GCP standards.

If the trial is prematurely terminated or suspended, the sponsor shall promptly inform the PI, the regulatory authorities, and the IRB/ERC of the reason for termination or suspension. Parents of children will be contacted immediately explaining why the study has been suspended or terminated and potential implications for children's safety, and provided with the opportunity to ask questions. Contacts with parents will be documented.

### **8.7. Future use of stored specimens**

Aliquots of participants' serum specimens will be maintained for five years after the completion of the study. This is to allow the samples to be stored long enough to support any requests for additional information from WHO or other agencies required to register CD-JEV for use. Following completion of this period, all samples will be destroyed if additional studies are not requested. The specimens will be stored at a long term storage facility determined by the Sponsor. No personal identifying information associated with the study will be stored on site with the specimens. After the data analysis for the study is complete, the master linking document will be destroyed, thus removing the possibility of identifying the individual from whom the data and sample were collected. Samples will not be used for unrelated, future studies without appropriate ethics committee approvals and consent from participants (if deemed required by ethics committees and the master linking document with identifiers has not yet been destroyed).

## **9. USE OF ANIMALS**

Not applicable. No animals will be used in this study.

## **10. COLLABORATIVE ARRANGEMENTS**

### **10.1. Publication policy**

A Clinical Study Report (CSR) comprised of text and results tables reflecting all safety and immunogenicity data will be generated. The CSR will be reviewed, approved, and signed by the investigator. The CSR will be compliant with ICH guidelines.

All data, documents, any recordings and information transferred by PATH to any contractor or obtained or prepared by any contractor, consultants, or persons associated by contractual relationships with any contractor during the trials, belong to icddr,b and PATH.

All confidential information communicated to the investigators by PATH shall be kept strictly confidential by them or any other person connected with the study and shall not be disclosed, either orally or in written form, to

any third party without prior written consent of the organization of which the information is the exclusive property.

Working with PATH representatives, the investigator is expected to publish the results of this research in a peer-reviewed scientific journal. In no way may anyone or any organization prohibit the public dissemination of valid results of this trial.

The International Committee of Medical Journal Editors (ICMJE) member journals have adopted a trials-registration policy as a condition for publication. This policy requires that all clinical trials be registered in a public trials registry. It will be the responsibility of PATH representatives to register this trial in an acceptable registry (CT.GOV). ICMJE authorship criteria will be strictly followed for publication of any manuscript(s) arising from this trial.

## **11. FACILITIES AVAILABLE**

Icddr,b has large multi-disciplinary international and national scientific research staff. Existing field, hospital, laboratory and office facilities will be used for this study. Icddr,b scientists have conducted a variety of vaccine studies (Polio, influenza, pneumococcal, cholera, Shigella, rotavirus, Japanese encephalitis, etc.).

### **11.1. Field site**

The study will be conducted in rural Matlab and urban Mirpur, Dhaka. Icddr,b has been maintaining a field research centre at Matlab for about fifty years. Due to the presence of ongoing HDSS, clinic and laboratory facilities, effective referral systems and well-established infrastructure at Matlab, it offers excellent research facilities for this study. The HDSS is a regularly updated information system on the approximate population of 220,000.

### **11.2. Laboratory facilities**

Existing laboratory facilities in icddr,b will be used to process the samples.

The specimens will be tested at the United States Army Medical Directorate, Armed Forces Research Institute of Medical Sciences, Bangkok, Thailand.

JE	Japanese encephalitis
PP	Per protocol
SAE	Serious Adverse Event
SD	Standard Deviation

2. Introduction

In 2012 PATH sponsored a double-blind, randomized controlled trial (PATH JEV05; icddr,b Protocol number 11050) among 818 Bangladeshi infants aged between 10 and 12 months to compare the immunogenicity of three lots of live attenuated SA 14-14-2 Japanese encephalitis vaccine (CD-JEV) manufactured in the Chengdu Institute of Biological Products (CDIBP) newly-constructed Good Manufacturing Practice (GMP) facility and one lot of CD-JEV manufactured in the pre-existing CDIBP facility.

The proposed study will enroll Bangladeshi children who previously participated in JEV05 to measure the persistence of the antibody response and determine if and when a booster dose of CD-JEV may be needed to maintain protective antibody levels. In addition, this study will determine the safety of a second dose of CD-JEV in this population.

2.1. Study Objectives

2.1.1. Primary Objective

To assess the long-term antibody response three and four years after primary CD-JEV vaccination of children who received a single dose of vaccine between 10 and 12 months of age.

2.1.2. Secondary Objectives

- To evaluate the antibody response following a booster dose of CD-JEV given at five years of age, among children who previously received a single dose of CD-JEV between 10 and 12 months of age.
- To determine the safety profile of a CD-JEV booster dose given to children four years after initial vaccination.

2.1.3. Exploratory Objectives

To describe the antibody response to a booster dose by differentiating between a primary and secondary antibody response at 7 days post-booster dose.

2.2. Study Design

This is a phase 4 open-label trial enrolling Bangladeshi children who previously participated in JEV05. Eligible participants who still live in the area will be identified using the local health and demographic surveillance system (HDSS) and asked to participate. Children will be divided into two groups based on whether they received vaccine from the old or new facility in the JEV05 study:

- Group A (up to 655 eligible): children randomized to Groups 2-4 (new facility) in JEV05.
- Group B (up to 163 eligible): children randomized to Group 1 (old facility) in JEV05.

A 2 mL blood sample will be collected from all JEV05 participants enrolled into this study three (Visit 01) and four (Visit 02) years after initial vaccination, respectively. The sera will be tested using a 50% plaque reduction neutralization test (PRNT-50); anti-Japanese encephalitis (JE) neutralizing antibody titer $\geq 1:10$ will be considered seroprotective.

Four years after receiving the initial dose of CD-JEV, eligible participants will be vaccinated with a single subcutaneous booster dose of CD-JEV. To evaluate the persistence of immunological memory, the response to this booster dose will be measured in a serum sample collected 7 (Visit 09) and 28 days (Visit 10) after vaccination. This sample will be tested for anti-JE neutralizing antibodies.

Following the booster dose, children will be monitored for immediate reactions during the first 30 minutes, solicited injection site and systemic adverse reactions for 7 days (Visit 02 – Visit 08), unsolicited adverse events (AEs) and serious adverse events (SAEs) for 28 days. All safety events will be identified or observed by study staff during home visits, clinic visits, and/or reported by a parent or legal guardian.

Solicited local and systemic adverse reactions will be assessed through home visits 1 through 6 days following vaccination, and a fixed site clinic (FSC) visit 7 days following vaccination. Information regarding unsolicited AEs occurring in the 28 days following vaccination will be collected and recorded on a standard questionnaire during clinic visits. Events will be graded for severity and assessed for relatedness to vaccination by the investigator.

A total of 10 visits is planned for this study. The schedule of study visits and activities is presented in Table 1 below.

No placebo control will be employed in this study and safety assessments will be unblinded.

The study will be conducted in the same sites as JEV05, i.e., Matlab and Mirpur (Dhaka).

Table 1. Outline of study visits and activities

Y3 after JEV05 ±3 months after enrollment in JEV05	Y4 after JEV05				
	Visit 01 (D0)	Visit 02 (D365±28)	Visit 03 through Visit 08 (D366-371±0)	Visit 09 (D372±3)	Visit 10 (D393±7)
Obtain informed consent	X				
Collect baseline demographic information	X				
Collect/review medical history	X	X			
Perform physical exam	X	X		X	X
Check inclusion/exclusion criteria	X	X			
Collect serum for long term response	X	X			
Administer booster dose of CD-JEV		X			
Collect serum for booster response				X	X
Observe for immediate reactions for 30 minutes		X			
Inquire about child's well being			X	X	X
Record reported adverse events		X	X	X	X
Record serious adverse events		X	X	X	X
Exit participant from study					X

2.3. Sample Size and Power

Since the study aims at following up with the participants of the JEV05 study who received a single dose of CD-JEV between 10 and 12 months of age, a maximum of 818 former JEV05 participants (up to 655 in Group A and up to 163 in Group B) is expected to be enrolled in this study. We anticipate an attrition rate from 10% to 40% in both groups, i.e. 10% to 40% of the subjects in Group A and Group B may not be enrolled into this study.

The precision (width) of the 95% confidence interval (CI) of the seroprotection rate before a booster vaccination is calculated based upon different assumptions on attrition rate and expected seroprotection rates and provided in Table 2.

Table 2. Precision of the 95% CI of the seroprotection rate according to attrition rate and seroprotection rate in each study group

Study Group	Expected seroprotection rate	Attrition rate			
		10%	20%	30%	40%
Group A	40%	0.079	0.084	0.089	0.096
	50%	0.080	0.085	0.091	0.098
	60%	0.079	0.084	0.089	0.096
	70%	0.074	0.078	0.084	0.090
	80%	0.065	0.068	0.073	0.079
Group B	40%	0.157	0.166	0.177	0.191
	50%	0.160	0.169	0.181	0.195
	60%	0.157	0.166	0.177	0.191
	70%	0.147	0.156	0.166	0.180
	80%	0.129	0.137	0.146	0.158

3. General Considerations for Data Analyses

All statistical tests will be two-sided with a significance level of 0.05. P-values will be recorded to 4 decimal places. All analyses will be conducted using SAS.

3.1. Analysis Set

All immunogenicity analyses will be performed on intention-to-treat (ITT) analysis set, which will be considered as the primary approach for immunogenicity analyses. The immunogenicity analyses will be also conducted on per protocol (PP) analysis set. Safety analysis will be conducted on participants who received a booster dose among the ITT population. Each analysis set is specified below.

3.1.1. Intention-to-Treat Analysis Set

For immunogenicity analysis on long-term assessment of the anti-JE antibody response to CD-JEV, the ITT analysis set will include all enrolled participants in this study whether the participants receive a booster dose of CD-JEV or not. The participants who have at least one serology result in Year 3 (Visit 01) or Year 4 (Visit 02) prior to the booster dose will be included in the long-term assessment.

For the immunogenicity analysis on antibody response following a booster dose of CD-JEV, the ITT analysis set will include those participants who receive the booster dose and have at least one serology result on 7 days (Visit 09) or 28 days (Visit 10) post booster vaccination.

3.1.2. Per Protocol Analysis Set

The PP analysis set will include the participants in the ITT set who comply with the protocol. For the long-term immunogenicity assessment, participants will be included in the PP analysis set if they meet eligibility criteria at Visit 01 (Year 3), have a valid serology result in Year 3 (Visit 01) and Year 4 (Visit 02) prior to the booster vaccination, and have no significant deviation in blood collection at the two time points.

For the immunogenicity analysis on antibody response following a booster dose of CD-JEV, participants will be included in the PP set if they meet eligibility criteria for the booster vaccination, have a valid serology result in Year 4 prior to the booster vaccination, receive the booster dose, have valid serology results on 7 days (Visit 09) and 28 days (Visit 10) post the booster dose, and do not significantly deviate in the scheduled blood collection post booster vaccination.

3.1.3. Safety analysis set

The safety analysis set will include all enrolled participants who receive a booster dose and will be used to analyze all safety measurements including reactogenicity (local and systemic signs and symptoms), AEs, and SAEs collected after a booster dose of CD-JEV.

3.2. Adjustment for Covariates

No adjustment for covariates is planned. However, longitudinal analysis may be performed for the long-term assessment of the anti-JE antibody response to CD-JEV as an ad-hoc analysis if necessary. If the longitudinal analysis is conducted, duration of follow-up since the initial vaccination will be included in the analysis as covariates. Other variables (e.g., gender, study site, nutrition status) as appropriate will be evaluated for inclusion as covariates as well. The longitudinal analyses will be considered exploratory and will not replace the primary planned analysis.

3.3. Missing Data and Outliers

3.3.1. Missing Data

All descriptive statistics will be performed on subjects with available data. Non-missing serology data are considered validated. Missing serology data are considered non-retrievable. Missing serology data will not be imputed and will be analyzed as if they were randomly missing.

If severity or relationship to the booster JE vaccine for a reported adverse event (AE) or serious adverse event (SAE) is missing, an independent category “Missing” will be reported.

If a start or stop date associated with a reported concomitant medication, AE or SAE is incomplete or missing, the following rules will be applied:

- If the day of the date is missing, use the day of the date of booster vaccination if start month and year are the same as those of date of the booster vaccination; otherwise use the 15th day of the month.
- If either month or year is missing, no imputations will be done.

If stop date for a concomitant medication/medical history (AE or SAE) is missing, the medication/medical history will be considered ongoing.

If the study termination date is missing, it will not be imputed.

If date of JE booster vaccination is incomplete or missing, the following rules will be applied:

- If day is missing, use the day of Visit 02 (Year 4) if start month and year are the same as those of date of Visit 02; otherwise use the 15th day of the month.
- If either month or year is missing, no imputation will be done.

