## 4. RESEARCH DESIGN AND METHODS

The proposed study is a phase 4 open-label trial enrolling up to 818 Bangladeshi children who had previously participated in JEV05, a PATH-supported clinical study conducted from May to December 2012 during which 10- to 12-month-old infants were given a single dose of CD-JEV. Eligible JEV05 participants who still live in the

area will be identified using the local health and demographic surveillance system (HDSS) and asked to participate. Children will be divided into two groups based on whether they received vaccine from the old or new facility in JEV05:

- Group A (up to 655 eligible): children randomized to Groups 2-4 (new facility) in JEV05.
- Group B (up to 163 eligible): children randomized to Group 1 (old facility) in JEV05.

An overview of the study activities is provided in Table 3. A 2 ml blood sample will be collected from all participants three and four years after initial vaccination. The sera will be tested using PRNT; JE neutralizing antibody titers  $\geq 1:10$  will be considered seroprotective.

After the blood draw at Visit 02 occurring in May to December 2016, four years after their initial vaccination, both groups will receive a single subcutaneous booster dose of CD-JEV. Additional serum samples will be collected on Day 7 and Day 28 following the booster dose for measurement of serum anti-JE neutralizing antibody titers.

Following the booster dose, children will be monitored for immediate reactions during the first 30 minutes, solicited injection site and systemic adverse reactions for 7 days, unsolicited adverse events and serious adverse events for 28 days. All safety events will be identified or observed by study staff during home visits, clinic visits, and/or reported by a parent or legal guardian. Solicited and systemic adverse reactions will be assessed through home visits 1 through 6 days following vaccination, and a fixed site clinic (FSC) visit on Day 7 following vaccination. Information regarding unsolicited AEs occurring in the 28 days following vaccination will be collected and recorded on a standard questionnaire during clinic visits. Events will be graded for severity and assessed for relatedness to vaccination by the investigator.

The study will be open-label; no placebo control will be employed and safety assessments will be unblinded.

[figure not shown]

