#### **4.4.6. Clinic follow-up visit (Visit 10, 28 days post vaccination $\pm 7$ days)**

A final study visit will be conducted 28 days after booster vaccination. The study team will:

- Inquire about the child's health (any illnesses or medications taken or visits to a healthcare facility).
- Inquire about any adverse events.
- Collect 2 ml of blood from participants with aseptic technique to detect anti-JE serum neutralizing antibody with the PRNT-50.
- Complete the appropriate section(s) of the CRF.
- Exit the participant from the study.

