**Table 4. Allowable Schedule**

Study Visit	Should occur	May occur
Visit 01	Three years after initial vaccination	Three years $\pm$ 3 months after initial vaccination
Visit 02	Day 365	One year $\pm$ 28 days after Visit 01
Visit 03	Day 366	1 day after booster vaccination
Visit 04	Day 367	2 days after booster vaccination
Visit 05	Day 368	3 days after booster vaccination
Visit 06	Day 369	4 days after booster vaccination
Visit 07	Day 370	5 days after booster vaccination

Study Visit	Should occur	May occur
Visit 08	Day 371	6 days after booster vaccination
Visit 09	Day 372	7 to 10 days after booster vaccination
Visit 10	Day 393	21 to 35 days after booster vaccination

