7.2. Analysis of Safety endpoints

- The number and proportion of participants with at least one occurrence of an immediate reaction (local or systemic reaction, unsolicited AE, and SAE) occurring within 30 minutes of the booster vaccination will be tabulated by study group. The severity, relationship to the booster vaccination, status at 30 minutes (ongoing or not), medication given, and total number of the immediate reactions will be summarized by study group as well. Proportion of participants

will be based on the number of participants who are in safety analysis set. In addition, the immediate reaction will be listed at the participant-level.

- The number and proportion of participants with at least one occurrence of local reactions (ecchymosis, erythema, edema, induration, and pain/tenderness) and with at least one occurrence of systemic reactions (fever, change in eating habits, diarrhea, sleepiness, irritability, unusual crying, and vomiting) occurring greater than 30 minutes after receipt of the booster dose through 7 days post vaccination will be summarized by study group along with 95% CI of the percent. Each specific local or systemic reaction will be summarized by severity for each study group. A listing including the local and systemic reactions at the participant-level will be provided as well.
- The number and proportion of participants with at least one unsolicited AE occurring within 28 days of the booster dose along with 95% CI of the proportion will be presented by study group. The AEs will be summarized by maximum severity and relationship to the booster vaccination for each study group. The total number, maximum severity, relationship to the booster vaccination, onset date, status/outcome, duration for resolved cases (resolution date – onset date + 1), and medication given of AEs will be also summarized by study group. Summaries will be repeated for AEs found to be related the booster vaccination. A listing of AEs at participant-level will be presented.

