- The number and proportion of participants with at least one SAE occurring within 28 days of the booster dose along with 95% CI of the proportion will be presented by study group. The SAEs will be summarized by maximum severity and relationship to the booster vaccination for each study group. The total number, maximum severity, relationship to the booster vaccination, onset date, status/outcome, duration for resolved cases (resolution date – onset date + 1), and medication given of SAEs will be also summarized by study group. Summaries will be repeated for SAEs found to be related the booster vaccination. A listing of SAEs at participant-level will be presented.
- A listing of concomitant medications at participant-level will be provided.

8. Summary of Changes to the Protocol

An interim analysis on immunogenicity assessment (anti-JE neutralizing antibody titer) collected at Visit 01 (Year 3 post primary vaccination) will be conducted in order to gain knowledge on whether or not a booster JE vaccine needs to be given sooner.

Reverse cumulative distribution curves for anti-JE neutralizing antibody titer will be produced at Year 3 and Year 4 post primary vaccination and 7 and 28 post booster vaccination to provide a visual presentation of the comparison of the antibody titers between study groups and how antibody titers change over time.

9. Reference

1. Wilson, E. B. (1927), Probable Inference, the Law of Succession, and Statistical Inference, *Journal of the American Statistical Association*, 22, 209–212.
2. Newcombe, R. G. (1998), Two-sided Confidence Intervals for the Single Proportion: Comparison of Seven Methods, *Statistics in Medicine*, 17, 857–872.
3. Newcombe, R. G. (1998), Interval Estimation for the Difference between Independent Proportions: Comparison of Eleven Methods, *Statistics in Medicine*, 17, 873–890.

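### SAP 3.3.1 fills missing days in AE start and stop dates with no ordering limit, so the SAP 7.2 duration can be zero or negative

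*SAP*

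**What the plan says.** SAP 3.3.1 Missing Data opens its date rules with "If a start or stop date associated with a reported concomitant medication, AE or SAE is incomplete or missing", so start and stop dates share one set of rules. If only the day is missing, the instruction is to "use the day of the date of booster vaccination if start month and year are the same as those of date" of the booster vaccination; in any other month the 15th is used. If month or year is missing, nothing is imputed. A missing stop date is treated as ongoing.

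SAP 7.2 Analysis of Safety endpoints plans, for unsolicited AEs and again for SAEs, a summary of "duration for resolved cases (resolution date – onset date + 1". It also counts participants with at least one unsolicited AE, and participants "with at least one SAE occurring within 28 days of the booster dose".

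Neither document requires an imputed stop to be on or after the onset, or an imputed onset to be on or before the stop. Neither removes or marks imputed dates in the duration summary. The SAP also does not say whether an imputed onset decides membership of the 28-day window.

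**The concern.** A fill-in day suited to a start date is not suited to a stop date. For a stop, the booster day is the earliest post-booster date that its month allows, so it precedes almost every onset in that month. For a start, the 15th of a later month may fall after a known stop. The written rule can therefore feed impossible values into a planned summary, and a programmer who follows the SAP has no stated way to prevent it.

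Booster safety is a secondary objective, and duration is a planned descriptor for AEs and SAEs. A few negative values would distort a mean or minimum, and repairs made at programming would not be pre-specified.

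A second point is conditional. If an imputed onset is used to decide the 28-day window, an event that was in the window can be moved out of it.

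**Working it through.** The plan gives no figure to reproduce, so the check applies the rule and the formula directly.

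**Inputs.** Fill-in rule: SAP 3.3.1. Duration D = stop - onset + 1: SAP 7.2. Onset window: Days 0 to 28. Booster dates: Protocol section 4, "After the blood draw at Visit 02 occurring in May to December 2016", taken as 1 May to 31 December (five 31-day and three 30-day months, 5 x 31 + 3 x 30 = 245 dates). Assumptions: every booster date and onset day has equal weight, and the true duration is 3 days (varied below). Grid: 245 x 29 = 7,105 cells.

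**When D is 0 or less.** This needs both dates in the same calendar month.
- Stop day missing, booster month: D = booster day - onset day + 1, which is 0 or less for every onset on Day 1 or later.
- Stop day missing, later month: D = 15 - onset day + 1, which is 0 or less when onset is on the 16th or later.
- Onset day missing, booster month: onset moves back to the booster day, so D is never below 1.
- Onset day missing, later month: D = stop day - 15 + 1, which is 0 or less when the stop is on or before the 14th.
- Both days missing: in the same month both get the same day, so D = 1; across months the stop stays later.

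**Worked dates.**
- Booster 2 May, onset 16 May (Day 14), stop in May with day unknown: stop becomes 2 May, D = 2 - 16 + 1 = -13.
- Booster 20 May, onset in June with day unknown, stop 9 June: onset becomes 15 June, D = 9 - 15 + 1 = -5.

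**Counts, true duration 3 days.**
- Stop day missing, booster month: onset after the booster day and at least two days before month end. A 31-day month has 29 x 28 / 2 = 406 such pairs and a 30-day month 28 x 27 / 2 = 378. Total 5 x 406 + 3 x 378 = 3,164.
- Stop day missing, later month: onset on day k, from the 16th to the 28th, with 29 - k eligible booster dates each: 13 + 12 + ... + 1 = 91 per month; 8 x 91 = 728.
- Together 3,164 + 728 = 3,892 of 7,105 (54.8%): 3,567 negative and 325 zero. The total is the same whether the rule's start month means the event's start month or the month of the date being filled.
- Onset day missing, later month: stop by the 14th means onset on the 1st to the 12th, so 28 + 27 + ... + 17 = 270 per month; 8 x 270 = 2,160 (30.4%).
- Both missing: 0.
- Onsets on Days 8 to 28 only (245 x 21 = 5,145 cells): 2,513 (48.8%) and 1,936 (37.6%).

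**Sensitivity to true duration (share with D of 0 or less).**

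| True duration (days) | Stop day missing | Onset day missing | Both missing |
|---|---|---|---|
| 2 | 57.9% | 32.2% | 0 |
| 3 | 54.8% | 30.4% | 0 |
| 5 | 48.5% | 26.5% | 0 |
| 7 | 42.2% | 22.1% | 0 |
| 14 | 20.1% | 3.2% | 0 |

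With durations of 1 to 28 days equally weighted (7,105 x 28 = 198,940 combinations), the shares are 46,702 (23.5%) and 19,880 (10.0%), and again none with both missing. The lowest values are -27 and -13 days.

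**The 28-day window, if imputed onset decides it.** Booster 10 May, true onset 3 June (Day 24), day missing: onset becomes 15 June, Day 36. That is past the last allowable Visit 10 (Protocol Table 4: "21 to 35 days after booster vaccination"). Each month contributes 14 such booster dates with 1 + 2 + ... + 14 = 105 cells. In all, 8 x 105 = 840 cells (11.8% of 7,105) from 112 booster dates move past Day 28, and 224 of them past Day 35. Inward moves need onsets after Day 28 to be recorded: none if Visit 10 is by Day 28, 242 of 490 cells if on Day 30, 707 of 1,715 if on Day 35. SAP 2.2 limits collection ("Information regarding unsolicited AEs occurring in the 28 days following vaccination will be collected"), as does Protocol section 4, but Protocol 4.4.6 says only "Inquire about any adverse events".

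**The case against.** The strongest objection concerns weight. No partial-date rate is given, and the protocol points to few such dates: daily home visits on Days 1 to 6 (4.4.4), times of onset and resolution collected (7.2.1), documentation that allows duration to be assessed (7.2.1.1), a recorded final date for events persisting at trial end (7.2.4), source review for completeness (7.6.1) and data clarification at close-out (7.8.4). Duration is one descriptive item with no test or decision attached, it is not planned for solicited reactions, and a negative value would probably be noticed in the listings. The 3-day duration has no source in the documents, and other choices give much lower shares. All of this stands, and it limits the point to minor. It does not supply the missing rule. The sponsor wrote a day-missing rule, so it foresaw such dates, and no contact is scheduled between Visit 09 (Days 7 to 10) and Visit 10 (Days 21 to 35).

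One could also read a partial stop date as ongoing. SAP 3.3.1 separates incomplete from missing dates, and the ongoing sentence covers only missing ones. Even on that reading, the failures with a missing onset day remain.

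The window argument is fairly called conditional. An outward move changes a participant's status only if all of that participant's in-window AEs move. A single inward move can create a case, but only if late onsets are recorded.

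**Conclusion.** The concern holds as a minor point. Followed as written, SAP 3.3.1 can produce zero or negative durations in the SAP 7.2 summaries of AEs and SAEs when exactly one of the two dates lacks its day, and never when both do. That conclusion follows from the rule itself and needs no assumption about frequency. The percentages do need assumptions (equal weights, the chosen true duration, a day already missing) and are not forecasts. The 28-day window issue is secondary and arises only if an imputed onset decides the count. Immunogenicity analyses are untouched.

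**What to change.** Amend SAP 3.3.1 and 7.2 as follows.
- **Stop date, day missing:** the imputed stop is never before onset and not after the last contact.
- **Onset date, day missing:** for events reported as post-booster, the imputed onset is not before the booster and not after a known stop date or the visit at which the event was reported.
- **Duration:** summarise only events with complete dates, or flag imputed durations.
- **28-day count:** state that an imputed onset alone does not remove an event collected as a post-booster AE, or report the count both ways for day-missing onsets.
- Keep the present rule of no imputation when month or year is missing.

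The cost is a few sentences, a small programming change and slightly fewer events in the duration summary. Ordering limits remove every zero and negative value but do not recover the true duration: with only a floor at onset, a true 3-day event with a missing stop day gets a mean of 4.8 days and a median of 1. Hence the complete-date or flagging rule. Capping onset at the reporting visit removes the 840 outward moves only if that visit is by Day 28, so the window statement is still needed. Counting any event whose reported month overlaps the window is not a useful substitute: if onsets up to Day 35 are recorded, misplaced cells fall only from 840 + 707 = 1,547 to 1,491.
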